## 6.2 Safety Variables

Safety will be assessed by evaluation of the following variables:

- Treatment-emergent adverse events (TEAEs; frequency, severity, seriousness, and relationship to study drug).

- Clinical laboratory variables (hematology, biochemistry including liver enzymes and total bilirubin, and urinalysis)
- Vital signs (systolic and diastolic blood pressure and pulse rate)

TEAE is defined as an AE observed after starting administration of the study drug and by visit 9 (day 30). If the adverse event occurs on Day 1 and the onset check box is marked “Onset after first study drug taken” or the onset check box is left blank, then the adverse event will be considered treatment emergent. If the adverse event occurs on Day 1 and the onset check box is marked “Onset before first study drug taken”, then the adverse event will not be considered treatment emergent. If a subject experiences an event both during the pre-investigational period and during the investigational period, the event will be considered as TEAE only if it has worsened in severity (i.e., it is reported with a new start date).

A study drug-related TEAE is defined as any TEAE with a causal relationship of YES by the investigator or with missing assessment of the causal relationship.

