10. The first dose of investigational product (IP)/study drug to be administered as soon as possible after the NC AKIRisk score is assessed between 2 and 22 hours after T0 is  $> 0.3$  (ng/mL) $^2/1000$  to allow completion of first treatment within 24 hours after T0. If the first dose of IP administration is completed within 8 hours after T0, the second dose of IP will be administered at 24 hours after T0 and the third dose of IP will be administered at 48 hours after T0. If the first dose of IP administration is completed past 8 hours after T0, the second dose of IP will be administered at 16 hours after the start of the first dose, and the third dose of IP will be administered at 40 hours after the start of the first dose of IP.  
Second and third dosing of the IP: a 2-hour treatment window before or after designated administration time is allowed.
11. Additional urine samples will be taken and stored to assess various clinical and compound related biomarkers.
12. AE will be collected from informed consent until visit 9 or until the subject is determined to be a screen failure. If the subject is discontinued from the study prior to visit 9, AEs will be collected until the EoS visit has been completed. After the end of all the procedures of visit 9 until visit 10, only serious AEs will be collected.
13. Assess data on renal replacement therapy, mortality, ICU stay, total hospital stay and duration of mechanical ventilation (time ventilation weaning, i.e., time from T0 to extubation).

*Footnotes continued on next page*

14. APACHE-II score is recorded on visit 2 preoperatively, postoperatively and during the time of drug administration at visits 2, 3 and 4 and at day 4 (visit 5) if the subject is still in the ICU. Results from local laboratory testing can be used, and the result closest to the indicated time points should be recorded.
15. Blood samples for pharmacokinetics will be collected at predose, at end of infusion and twice after study drug administration at 2 to 4 hours postdose and at 4 to 12 hours postdose of first administration, at end of infusion of second administration, and at predose and at end of infusion of third administration.
16. Blood samples for gene expression measurements will be collected at predose and 2 to 4 hours postdose of first and third administrations.

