**Table 5 Prognostic Factor Analysis Arm**

Treatment Group Code (ARMCD)	Prognostic Factor Analysis Arm (Labels in TLFs)	
P	NC positive	
O	NC negative	Total (PFAS)

ARMCD: Planned Arm Code; TLFs: Tables, Listings and Figures; NC: NephroCheck; PFAS: Prognostic Factor Analysis Set

- Duration of CPB

Duration of CPB in hours is defined as: ‘Time of T0’ - ‘Time of Onset CPB’.

- Duration of Aortic Cross-Clamp

Duration of Aortic Cross-Clamp in hours is defined as: ‘End Time of Aortic Cross-Clamp’ - ‘Start Time of Aortic Cross-Clamp’.

- Duration from Incision to Closing of Skin

Duration from Incision to Closing of Skin in hours is defined as: ‘Time of Closing of Skin’ - ‘Time of Incision of Skin’.

- Duration of Study

Duration of Study in days is defined as: ‘Date of the last date of completed or discontinued recorded in eCRF period status forms’ - ‘Date of Surgery’ + 1.

- Previous and Concomitant Treatment (Medication and Non-Medication Therapy)

Previous medication is defined as medication with at least one dose taken before the date of the screening.

Concomitant medication is defined as medication with at least one dose taken between the screening (inclusive) and surgery, and following surgery to EoS.

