- Proportion of subjects with renal recovery, defined as a SCr value at hospital discharge equal to or lower than that at baseline

The following analysis will be conducted for endpoint group 2.

- Descriptive statistics will be presented.
- The endpoint will be analyzed using the Wilcoxon-test.

Group 2:

- Number of hospital days during initial hospitalization
- Number of ICU days during initial hospitalization
- Total number of hospital days up to day 90
- Total number of ICU days up to day 90
- Duration of AKI based on AKI stage using SCr (Duration of AKI-SCr72h and Duration of AKI-SCr7d)

The following analysis will be conducted for endpoint group 3.

- The number and percentage of category will be presented.
- The endpoints will be analyzed using the Wilcoxon-test.

Group 3:

- Severity of AKI within 72 hours after T0
- Severity of AKI within 7 days after T0
- Number of readmissions to ICU (use “0 Times”, “1 Time”, “2 Times” and “3 Times or More” as category)
- Number of readmissions to hospital (use “0 Times”, “1 Time”, “2 Times” and “3 Times or More” as category)

The following analysis will be conducted for endpoint group 4.

- Time to event will be analyzed using Kaplan-Meier method. Kaplan-Meier estimator (1st Quartile, Median, 3rd Quartile, their 90% confidence intervals [CIs] and Range) will be presented. For AKI-SCr72h, subjects without developing AKI-SCr72h will be censored at the date of Visit 5 (Day 4, 72 hours after T0) or at the date of discontinuation if the subjects discontinue before Visit 5. For AKI-SCr7d, subjects without developing AKI-SCr7d will be censored at the date of Visit 8 (Day 7/DoD), at Day 7 if the Visit 8 (Day 7/DoD) assessment was not performed but still in the study or at the date of discontinuation if the subjects discontinue before Visit 8. For ventilator weaning, subjects who discontinued the study without ventilator weaning will be censored at the date of discontinuation.
- Time to event will be analyzed using the log-rank test.
- Hazard ratio and its 90% CI will be presented Based on Cox proportional hazards model with treatment as the only explanatory variable.

Group 4:

- Time to AKI-SCr72h
- Time to AKI-SCr7d
- Time to ventilator weaning, defined as the time from T0 to extubation (i.e., removal of the endotracheal ventilation tube)

The following analysis will be conducted for endpoint group 5.

- Descriptive statistics for the variables and changes from baseline at each visit will be presented.

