The number of TEAEs and the number and percentage of subjects with TEAEs, as classified by SOC and PT will also be summarized by severity using National Cancer Institute-Common Terminology Criteria for Adverse Events (NCI-CTCAE). In the subject count, if a subject has multiple TEAEs with the same SOC or PT, but with differing NCI-CTCAE Grade, then the subject will be counted only once with the worst NCI-CTCAE Grade, however, if any of the NCI-CTCAE Grade values are missing then the subject will be counted only once with missing NCI-CTCAE Grade. In the adverse event count, the adverse events will be presented in each category they were classified to. Drug related TEAEs will be presented in a similar way by NCI-CTCAE Grade.

The number and percentage of subjects with TEAEs, as classified by SOC and PT will be summarized for each treatment group by time interval. For each adverse event in a particular interval, a subject will be counted if there is an onset of a treatment-emergent adverse event regardless of onset in other intervals.

Time intervals will be categorized according to the following categories:

- $\geq 0$  hours to  $\leq 24$  hours after T0
- $> 24$  hours to  $\leq 48$  hours after T0
- $> 48$  hours to  $\leq 72$  hours after T0
- $> 72$  hours after T0 to  $\leq$  Day 7 or DoD
- $>$  Day 7 or DoD to  $\leq$  Day 30

The number and percentage of subjects with TEAEs, as classified by SOC and PT will be summarized for each treatment group by subgroups defined in [Section 7.8].

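### SAP 6.2 ties the treatment-emergence check box to Day 1 (the day of surgery), but the first dose can fall on Day 2, so a surgery-day event with a blank box is called treatment emergent before any drug was given

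*SAP*

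**What the plan says.** SAP 6.2 opens with the definition: "TEAE is defined as an AE observed after starting administration of the study drug and by visit 9 (day 30"). An operational rule based on an onset check box follows. It begins "If the adverse event occurs on Day 1 and the onset check box is marked" to show onset after the first dose, or if "the onset check box is left blank, then the adverse event will be considered treatment emergent". The companion sentence, also confined to Day 1, covers the opposite mark: "Onset before first study drug taken”, then the adverse event will not be considered treatment emergent". No sentence says what the box does on any other date. The same section counts a treatment-emergent event with a missing causality assessment as drug-related.

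The SAP does not define Day 1, but its day counts agree with one another:

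- Table 1 puts Visit 3 on Day 2, at T0 + 24 hours.
- Section 7.4.4 has subjects "censored at the date of Visit 5 (Day 4, 72 hours after T0").
- Duration of study in section 6.5 subtracts "Date of Surgery’ + 1".
- Time to AKI in section 6.1.3 is a date minus the date of T0, plus 1.

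On first-dose timing, SAP Table 1 footnote 10 asks for dosing as soon as possible after a positive NephroCheck, "to allow completion of first treatment within 24 hours after T0". Protocol 2.2.1 keeps an 8-hour limit for subjects positive at 2 to 6 hours and allows 24 hours for those positive later. SAP 7.3.1 tabulates first doses given after T0 + 8 hours, and Table 12 makes them a subgroup.

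**The concern.** A rule tied to Day 1 works only if the first dose is on Day 1. Once the first dose can fall on the next calendar day, the date on which the box takes effect and the date on which it is needed can differ. SAP versions 3.00 and 4.00 both postdate Protocol Version 2.0 and list analyses added to assess that amendment, but neither lists a change to the treatment-emergence rule.

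The events at risk are in the database. Protocol 5.5.1 starts adverse event collection at consent, and Protocol 2.2.1 has the indication for a reoperation recorded as an adverse event. If such events precede the first dose and are still counted, they add drug-independent events to both arms of the main safety tables and dilute any real difference. Some could also enter the drug-related tables through the missing-causality rule.

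**Working it through.** No figure in the plan depends on this rule, so there is none to reproduce. The check is a reading of the text plus clock arithmetic.

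**Step 1: which date is Day 1?** Day 2 is T0 + 24 hours and Day 4 is T0 + 72 hours, so Day 1 is T0 + 0, the day of surgery. The two date formulas give the value 1 on the date of surgery and on the date of T0 respectively. No passage ties Day 1 to the first dose.

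**Step 2: can the first dose fall on Day 2?** Let T0 be at clock hour h. A dose can be completed after midnight if h + limit > 24.

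- 24-hour limit: h + 24 > 24 for any T0 after midnight, so always possible.
- 8-hour limit: h + 8 > 24 requires T0 after 16:00, so possible only for late surgery.

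**Step 3: how much of the late window lies on Day 2?** The window from T0 + 8 to T0 + 24 hours is 16 hours long. For h up to 16, the part after midnight is h hours, so the share is h/16. The T0 clock times are assumptions, because the documents give none.

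| Assumed T0 | Hours of the window on Day 2 | Share |
|---|---|---|
| 08:00 | 8 of 16 | 50% |
| 10:00 | 10 of 16 | 62.5% |
| 12:00 | 12 of 16 | 75% |
| 14:00 | 14 of 16 | 87.5% |
| 16:00 or later | 16 of 16 | 100% |

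These are shares of late first doses only if doses are spread evenly over the window.

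**Step 4: apply the rule.** Take an assumed T0 at 14:00 and a first dose at 09:00 the next day, which is T0 + 19 hours.

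- *Event at 20:00 on the day of surgery, box blank.* It is a Day 1 event, so the blank-box clause makes it treatment emergent. Its onset is 13 hours before the first dose, so the opening definition says it is not. The two sentences contradict each other.
- *The same event, box marked 'before'.* The Day 1 rule excludes it. No conflict.
- *Event at 03:00 on Day 2, box marked 'before'.* The Day 1 rule does not apply and the mark has no stated effect. The opening definition excludes the event if onset time or the box is used. A comparison of dates alone cannot, because event and first dose share a date.

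**Step 5: causality.** If the first event above also has no causality assessment, the section's last rule makes it drug-related.

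**The case against.** The strongest reply is that the opening sentence of SAP 6.2 governs and the check-box sentences only break ties. On that view a Day 2 event before the first dose fails the definition whatever the box rule omits, and the hour-based intervals in section 7.5.1 imply that onset times exist. This largely answers the Day 2 case: it is a gap, not a stated error, and it closes if onset time or the box is used. It does not answer the surgery-day case with a blank box, where the SAP gives an explicit instruction that conflicts with its definition.

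It can also be said that Day 1 is undefined and could be programmed as the first-dose date. That would remove the problem, but no passage supports that reading and the SAP's day counts point the other way.

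Four stronger readings are tempting and should not be drawn:

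- *That the T0-based intervals cause misclassification.* Under section 7.5.1, "a subject will be counted if there is an onset of a treatment-emergent adverse event regardless of onset in other intervals", so the intervals hold only events already classed as treatment emergent.
- *That Protocol Version 2.0 created the problem.* An 8-hour limit already crosses midnight when T0 is after 16:00. The 24-hour limit makes a Day 2 first dose more common.
- *That 75% to 100% of late first doses are affected.* That range needs T0 at noon or later and evenly spread dosing. Earlier T0 times give 50% to 62.5%, and dosing as soon as possible after a positive test could lower the share further.
- *That T0 intervals hide the infusion-site reactions expected from phase 1.* Protocol 1.3 says those reactions occurred on average after 5 days of repeated infusion, and no onset time is given for feeling hot.

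**Conclusion.** The concern holds as a wording error with one definite wrong result and one gap. The definite result is that a surgery-day event with a blank box, in a subject first dosed on the next calendar day, is classed as treatment emergent against the SAP's own definition. The gap is that a 'before' mark on Day 2 has no stated effect.

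The size cannot be computed. It depends on T0 clock times, the share of subjects dosed late and the blank-box rate, none of which is given. The percentages above describe where late doses would fall under even spacing; they are not misclassification rates, since completed boxes on Day 1 are honoured.

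A reader might infer a bias for or against the drug. The documents do not support that: allocation is randomised and blinded, so the expected effect is higher counts in both arms and a diluted contrast. Safety summaries are descriptive, and no efficacy result or stopping rule is touched. The conclusion rests on Day 1 being the day of surgery, which is inferred from consistent day counts and not from a definition. The correction is worth making because it removes a stated rule that gives a wrong classification, at almost no cost.

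**What to change.** In SAP 6.2:

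1. Replace Day 1 with the date of first study drug administration throughout the check-box rule.
2. State that adverse events dated before that date are not treatment emergent.
3. Let a blank box count as treatment emergent only on that date.

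The cost is SAP wording and programming before database lock and unblinding. The check box and first-dose timing are already recorded (SAP 6.2 and 7.3.1, Protocol 5.1.4), so no new data are needed.

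Optionally, add to section 7.5.1 an interval table timed from the start of the first dose, beside the T0-based one. A subject first dosed between T0 + 8 and T0 + 24 hours has between 16 and 0 hours of exposure in the 0-to-24-hour interval, so the extra table would show time since dosing more clearly. It is an addition, not the correction of an error.

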### **6.3 Pharmacokinetic Variables**

- ASP1128 plasma concentrations

### **6.4 Pharmacodynamic Variables**

- Target gene expression

### **6.5 Other Variables**

- Randomization Arms

[Table 4] presents the groups to which subjects are randomized. The Randomization Arms will be used for analysis of efficacy, safety, pharmacokinetics and pharmacodynamics.

**Table 4 Randomization Arm**

Treatment Group Code (ARMCD)	Randomization Arm (Labels in TLFs)	
A	ASP1128	
P	Placebo	Total (Randomization)

ARMCD: Planned Arm Code; TLFs: Tables, Listings and Figures

- Prognostic Factor Analysis Arms

[Table 5] presents the groups to which subjects are in PFAS. The Prognostic Factor Analysis Arms will be used for analysis of demographic and other baseline characteristics for Observational Cohort.

**Table 5 Prognostic Factor Analysis Arm**

Treatment Group Code (ARMCD)	Prognostic Factor Analysis Arm (Labels in TLFs)	
P	NC positive	
O	NC negative	Total (PFAS)

ARMCD: Planned Arm Code; TLFs: Tables, Listings and Figures; NC: NephroCheck; PFAS: Prognostic Factor Analysis Set

- Duration of CPB

Duration of CPB in hours is defined as: ‘Time of T0’ - ‘Time of Onset CPB’.

- Duration of Aortic Cross-Clamp

Duration of Aortic Cross-Clamp in hours is defined as: ‘End Time of Aortic Cross-Clamp’ - ‘Start Time of Aortic Cross-Clamp’.

- Duration from Incision to Closing of Skin

Duration from Incision to Closing of Skin in hours is defined as: ‘Time of Closing of Skin’ - ‘Time of Incision of Skin’.

- Duration of Study

Duration of Study in days is defined as: ‘Date of the last date of completed or discontinued recorded in eCRF period status forms’ - ‘Date of Surgery’ + 1.

- Previous and Concomitant Treatment (Medication and Non-Medication Therapy)

Previous medication is defined as medication with at least one dose taken before the date of the screening.

Concomitant medication is defined as medication with at least one dose taken between the screening (inclusive) and surgery, and following surgery to EoS.

## **7 STATISTICAL METHODOLOGY**

### **7.1 General Considerations**

- For continuous variables, descriptive statistics will include the number of subjects (n), mean, standard deviation (SD), median, minimum and maximum. The number of digits to be used for the mean, standard deviation and median will be added one more digit to raw data with rounding off. The minimum and maximum will be presented with the same number of digit(s) as raw data. In addition, for pharmacokinetics (PK) variables, the coefficient of variation (CV) and the geometric mean will also be calculated.

Frequencies and percentages will be displayed for categorical data. Percentages by categories will be based on the number of subjects with no missing data, i.e. will add up to 100%. Frequencies and percentages will be rounded to one decimal place. For time-to-event variables, the number and percentage of subjects with the event using Kaplan-Meier method, the cumulative event rate will be estimated and a plot will be constructed.

- Summaries based on FAS and PPS (e.g. disposition, baseline and efficacy data) will be presented by planned randomization arm, unless specifically stated otherwise. Safety analysis and other summaries based on SAF will be presented by actual treatment received. Analysis of Observational Cohort based on PFAS will be presented by prognostic factor analysis arm.
- All statistical comparisons will be made using two sided tests at the  $\alpha=0.10$  significance level unless specifically stated otherwise. All null hypotheses will be of no treatment difference, all alternative hypotheses will be two-sided, unless specifically stated otherwise.
- All data processing, summarization, and analyses will be performed using SAS® Version 9.4 or higher on Red Hat Enterprise Linux. Specifications for Table, Figures, and Listings can be found in the TLF specifications for this study.
- For continuous variables that are recorded as “ $<X$ ”, “ $\leq X$ ”, “ $>X$ ”, or “ $\geq X$ ”, the value of “ $X$ ” will be used in the calculation of summary statistics if otherwise noted. The original values will be used for the listings.
- MedDRA will be used as the coding dictionary for adverse event and medical history.
- WHODrug Global B3 will be used as the coding dictionary for previous and concomitant medication.
- For the definition of subgroups of interest please refer to [Section [7.8](#)].

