#### **Primary Efficacy Analysis:**

The primary efficacy endpoint of AKI (AKI-SCr72h) proportion will be analyzed using the Cochran-Mantel-Haenszel (CMH) test with strata to control for baseline eGFR ( $< 45, \geq 45$ ) on the Full Analysis Set (FAS). The FAS is defined as all randomized subjects who receives at least 1 dose of study treatment (ASP1128 or placebo), and the analysis is based on the randomized treatment. The Mantel-Haenszel (MH) estimate of the common risk ratio and 2-sided 90% confidence interval will be calculated.

The hypothesis testing on the primary analysis will be performed at 2-sided 0.10 significance level to test the null hypothesis that AKI-SCr72h proportion is equal between the 2 treatment arms versus the alternative hypothesis that AKI-SCr72h proportion is different between the ASP1128 arm vs the placebo arm.

The supplementary analysis for the primary efficacy endpoint will be performed on the Per Protocol Set, which includes all subjects in the FAS and do not have any major protocol deviations.

As sensitivity analysis, chi-square test will be performed to evaluate the appropriateness of CMH test with strata to control for baseline eGFR ( $< 45, \geq 45$ ). The estimate of the unadjusted risk ratio and 2-sided 90% confidence interval will be calculated.

Additional sensitivity analysis will be performed to evaluate the impact on the analysis of AKI-SCr72h proportions due to any missing data/assessments and any loss to follow-up.

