#### **5.2.1 Reasons for Exclusion From PPS**

The following reasons may lead to subject's exclusion from PPS:

1. Not complete scheduled three times administrations of study drugs
2. Administration of excluded concomitant treatment as described in the protocol
3. Violation of the any inclusion or exclusion criteria

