### **7.2.2 Protocol Deviations**

Protocol deviations as defined in the study protocol (Section 8.3 Major Protocol Deviations) will be assessed for all registered subjects. The number and percentage of subjects meeting any criteria will be summarized for each criterion and overall, by randomization arm and NC negative group as well as by study site. Subjects deviating from a criterion more than once will be counted once for the corresponding criterion. Any subjects who have more than one protocol deviation will be counted once in the overall summary. A data listing will be provided by site and subject.

The protocol deviation criteria will be uniquely identified in the summary table and listing. The unique identifiers will be as follows:

- PD1 - Entered into the study even though they did not satisfy entry criteria,
- PD2 - Developed withdrawal criteria during the study and was not withdrawn,
- PD3 - Received wrong treatment or incorrect dose,
- PD4 - Received excluded concomitant treatment.

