## **7.5 Analysis of Safety**

[Analysis population: SAF, Analysis group: Randomization Arm and Total]

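### The SAP assigns safety data to actual treatment in 7.1 but to the randomised arm in 6.5 and the SAF headers; separately, the PPS exclusion list omits wrong treatment

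*SAP*

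**What the plan says.** **Grouping of safety data.** SAP 7.1 has two consecutive sentences on grouping. For FAS and PPS summaries, results "will be presented by planned randomization arm, unless specifically stated otherwise". For safety, "Safety analysis and other summaries based on SAF will be presented by actual treatment received".

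SAP 6.5 introduces the Randomization Arms through Table 4, which "presents the groups to which subjects are randomized", and adds: "The Randomization Arms will be used for analysis of efficacy, safety, pharmacokinetics and pharmacodynamics". The footnote to Table 4 expands ARMCD as the planned arm code. The header of SAP 7.5, above all the safety output, reads "Analysis population: SAF, Analysis group: Randomization Arm and Total". SAP 7.2.5 (duration of study) and 7.3.1 (exposure) carry the same header. SAP 7.2.3 (baseline tables) lists the SAF with other analysis sets, also by Randomization Arm.

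**Per Protocol Set.** SAP 5.2.1 gives three possible reasons for exclusion: "Not complete scheduled three times administrations of study drugs", use of excluded concomitant treatment, and a breach of an entry criterion. SAP 7.2.2 and protocol 8.3 list four major deviations, among them "PD3 - Received wrong treatment or incorrect dose". The protocol synopsis describes the PPS as the set "which includes all subjects in the FAS and do not have any major protocol deviations". Protocol 7.2.2 instead leaves the exclusion criteria to the SAP.

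**The concern.** A safety table should have one rule for where a subject's events go when the drug received differs from the drug assigned. Here the general section gives one rule, and the variable definition and the output headers give another. If the headers are followed, an adverse reaction in a placebo-assigned subject who was given ASP1128 appears in the placebo column. Two programmers working from this SAP could produce different tables, and the choice might then be made after the data are known.

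The PPS is the robustness check on the FAS result. A subject who received three administrations of the wrong drug, took no excluded medication and met the entry criteria matches none of the reasons in 5.2.1. That subject would be analysed under the planned arm, unless another document removes them.

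**Working it through.** The plan states no figure on this point, so the main check is a comparison of text.

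**Step 1: can the safety rules be reconciled?**

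| Place in SAP | Grouping for SAF or safety |
|---|---|
| 7.1 | Actual treatment received |
| 6.5 and Table 4 | Randomization Arm, planned arm code |
| 7.2.3 | Randomization Arm (SAF listed with FAS, PPS, PKAS and PDAS) |
| 7.2.5 | Randomization Arm |
| 7.3.1 | Randomization Arm |
| 7.5 | Randomization Arm |

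In 7.1 the clause allowing exceptions stands in the FAS/PPS sentence. The safety sentence has no such clause, so the 7.5 header is not a permitted exception. Section 6.5 defines the Randomization Arm as planned, so the term cannot mean actual treatment. The SAP defines no actual-treatment variable with which to carry out 7.1. The protocol does not settle the matter: 7.2.1 ties the FAS to randomised treatment, 7.2.3 is silent for the SAF, and the synopsis says only that safety is summarised by treatment.

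**Step 2: which major deviations does 5.2.1 cover?**

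| Deviation | Reason in 5.2.1 |
|---|---|
| PD1, entry criteria | Yes |
| PD2, met withdrawal criteria but stayed | None |
| PD3, wrong treatment or incorrect dose | None |
| PD4, excluded concomitant treatment | Yes |

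The remaining reason, incomplete dosing, is not one of the four deviations. The list is therefore narrower than the synopsis by PD2 and PD3.

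**Step 3: size in the safety tables.** Inputs: 110 per arm (SAP 4), and k misallocated subjects, where k = 1 to 3 is an assumption because the documents give no rate. The largest shift in one arm's event rate is k/110: 1/110 = 0.9 points and 3/110 = 2.7 points.

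**Step 4: size in the PPS.** Inputs: 60% in placebo and relative risk 0.7 (SAP 4), giving 0.7 × 60% = 42% and a difference of 18 points. Assume whoever receives ASP1128 gets its full effect.

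- k placebo-assigned subjects fully crossed over among 110 reduce the difference by 18 × k/110: 0.16 points for k = 1 and 0.49 points for k = 3.
- For swaps in both directions, assume 99 per arm (110 less 10%). With k swapped each way, the risk ratio is [0.42(99 − k) + 0.60k] / [0.60(99 − k) + 0.42k]. For k = 1 this is 41.76/59.22 = 0.705; for k = 2, 41.94/59.04 = 0.710; for k = 5, 42.48/58.50 = 0.726. The true value is 0.700.

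**The case against.** On safety, the best defence is that 7.1 is the only place that addresses assignment for SAF summaries and that it is unqualified. On this view the bracketed headers merely choose a set of table columns, as distinct from the prognostic-factor columns of Table 5. The SAF definition in 5.3 also omits the randomised-treatment clause that the FAS definition carries, and the text under 7.5 speaks only of treatment group. This shows that 7.1 is probably what was intended. It does not remove the conflict, because 6.5 defines the Randomization Arms by assignment and expressly applies them to safety.

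On the PPS, the defence is stronger. A reader might infer that the SAP requires misdosed subjects to be kept. No text says so. Section 5.2.1 introduces its reasons as ones that may lead to exclusion, and both documents refer detailed criteria to Classification Specifications that are not available here. The dosing reason might also be stretched to a subject who never received the assigned drug. Protocol 7.2.2 authorises the SAP to set the list, so part of the mismatch lies within the protocol itself. What stands is an omission measured against the synopsis.

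A reader might also infer that PD3 is the deviation that dilutes the PPS effect most. The documents give no counts to support that, PD3 includes dose errors that are not crossovers, and the shifts calculated above are small. PD3 cases would also be visible, since SAP 7.2.2 summarises and lists them.

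**Conclusion.** The contradiction in the safety grouping rule is real and should be corrected. The PPS point holds only as an omission: PD3 and PD2 are not listed for exclusion although the synopsis would remove them, and the Classification Specifications may already deal with this.

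Nothing changes if nobody is misdosed. If someone is, a safety rate moves by up to 0.9 percentage points per misallocated subject, on the assumption of about 110 per arm. One to three one-way crossovers would take about 0.2 to 0.5 points off an 18-point PPS difference, assuming a full drug effect in those treated. The primary analysis is not touched: the FAS is analysed by randomised treatment in both documents, and protocol 7.4 bases interpretation on it. This is a low-severity point, worth making because the correction is cheap and should be settled before unblinding.

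**What to change.** 1. State one rule for SAF summaries: actual treatment received, as in SAP 7.1.
2. Define an actual-treatment variable beside Table 4. Say how a subject with mixed exposure over the three administrations is classified, and that an incorrect dose of the assigned drug does not by itself change the group.
3. Reword 6.5 so that the Randomization Arms no longer govern safety, and align the SAF headers in 7.2.3, 7.2.5, 7.3.1 and 7.5. The 7.2.3 header also covers the FAS and PPS, so it needs splitting rather than replacing.
4. Add PD3 to 5.2.1, and reconcile the list, including PD2, with the synopsis. Check the result against the Classification Specifications.

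The cost is a short text revision of the SAP and one derived variable. Protocol 5.1.4 already has the prepared and actual dose and the schedule recorded, so the change should need little or no new data collection. Editing only 6.5, 7.5 and 5.2.1 would leave the other three headers in conflict with 7.1.
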